# **Statistical Analysis Plan**

#### Sample Size and Power Calculations

We will evaluate, based on a 20% attrition rate, a total of 1,120 participants at 12-month postenrollment data collection time point, which will be the main time point for the comparison of primary outcomes. We will use a randomization ratio of 2:2:1 (High-Touch; High-Tech; ODP, respectively) and, as such, estimate final sample sizes of n=448 for each active care strategy and n=224 for the ODP strategy. All calculations for the power estimates were done in PASS version 13. For the primary test for the trial, the power calculation is based on the comparison of the two primary care strategies (High-Touch and High-Tech) for the main outcome of hospital readmissions between the strategies, using a two-sample test of proportions; specifically we have 80% power to detect a difference between a readmission rate of 20% in the High-Touch care strategy versus 28% in the High-Tech care strategy. Additionally, for the overall differences between the three care strategies the given sample sizes yield 95% power; based on a chi-squared test.

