For the tests of interactions, we have identified, a priori, eight subgroups of interest: those aged 60 years and above, constituting 23% of the sample, and those aged below 60; race with non-white participants constituting 38% of the sample (n=203 High-Touch/High-Tech, n=100 ODP), and white participants; Charlson Comorbidity Index Score of five or above, indicating higher illness complexity includes 54% of the sample versus lower illness complexity; and positive (opposed to negative) for comorbid behavioral health conditions for 60% of the sample. We are only presenting power analysis results for the treatment by age interactions since we do not have any a-priori hypotheses about the direction of differential effects for treatment by race, treatment by illness complexity, or treatment by comorbid behavioral health condition. All such interactions will therefore be labeled as purely exploratory in subsequent findings and publications. Power estimates for interactions were calculated based on a 2-way factorial design and the average sample size across groups. For readmission rates, we used a normal approximation to estimate the standard deviation and applied a 2-way ANOVA as similar procedures are not available for dichotomous outcomes without approximating as normal.

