For age by treatment interactions, readmission rates are hypothesized to increase in older age groups, with greater differences in the treatment effects. We also hypothesized that the intervention groups will yield similar rates in the younger group while High-Tech will be closer to ODP in the older group. More specifically, we have 79.8% power to detect a significant interaction with readmission rates of 22%, 40%, and 42% in the older group (for High-Touch, High-Tech, and ODP, respectively) and rates of 18%, 16% and 28% in the younger group. For PAM scores, we hypothesized that, in the older group, the interventions will work equally well and much more effectively than ODP, whereas, in the younger group, High-Tech will be most effective, with High-Touch and ODP showing no effect on PAM scores. More specifically, we have 72.2% power to detect a significant interaction with mean increases in PAM of 8, 8, and 1 in the older group for High-Touch, High-Tech, and ODP, respectively, and mean increases of 0, 8 and 0 in the younger group. For SF-36 scores, we assumed a greater overall effect for High-Touch and speater effect in younger ages and a slightly larger difference between ages for the

High-Touch group. Specifically, we have 99.5% power to detect a significant interaction with mean increases in SF-36 of 7, 2, and 0 in the older group for High-Touch, High-Tech, and ODP, respectively, and mean increases of 15, 8, and 1 in the younger group.

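### The age-by-treatment interaction powers are for six equal cells, not the plan's 23% older and 2:2:1 design, and their inputs do not average to the main-effect inputs

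*Combined protocol and SAP*

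**What the plan says.** All of this is in the SAP under Sample Size and Power Calculations, unless another section is named.

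- **Design.** 1,120 evaluable participants at 12 months, allocated 2:2:1, giving 448 High-Touch, 448 High-Tech and 224 ODP. The older subgroup is "those aged 60 years and above, constituting 23% of the sample".
- **Interaction method.** "Power estimates for interactions were calculated based on a 2-way factorial design and the average sample size across groups". Readmission is handled by a normal approximation in a two-way ANOVA; the SD used is not given.
- **Interaction powers.**
  - Readmission: "we have 79.8% power to detect a significant interaction with readmission rates of 22%, 40%, and 42% in the older group", with 18%, 16% and 28% in the younger group.
  - PAM: "we have 72.2% power to detect a significant interaction with mean increases in PAM of 8, 8, and 1" in the older group, with 0, 8 and 0 in the younger.
  - SF-36: "we have 99.5% power to detect a significant interaction with mean increases in SF-36 of 7, 2, and 0 in the older group", with 15, 8 and 1 in the younger.
- **Main-effect inputs.** For the test the plan calls primary: "a readmission rate of 20% in the High-Touch care strategy versus 28% in the High-Tech care strategy", at 80% power. PAM gains are 4, 8 and 0.5 (SD 20.9) and SF-36 gains are 11, 5 and 0 (SD 10), for High-Touch, High-Tech and ODP in that order. No overall ODP readmission rate is given.
- **PAM in words.** In older participants the two active strategies are to work equally well; "in the younger group, High-Tech will be most effective, with High-Touch and ODP showing no effect on PAM scores".

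Quantitative Analysis adds that age is the only interaction being powered, that interactions are tested two-sided at 0.05, and that logistic models use likelihood ratio tests.

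**The concern.** There are two linked problems.

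First, averaging the sample size over the six cells replaces the trial's unequal cells with equal ones. An interaction is estimated less precisely when one level of the subgroup factor is small, and here only 23% are older. The plan nevertheless presents the results as powers the trial has.

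Secondly, each arm's overall rate or mean must be the age-weighted average of its subgroup values. If the main-effect and subgroup inputs agree only at an age mix the plan does not expect, they describe two different trials. A reader then cannot tell which one the primary comparison was sized for. Accurate power also affects how a null age interaction is read, particularly for PAM.

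**Working it through.** **Formula.** For a 2×3 layout with older share *a* and arm shares *w*, let *g* be each arm's older-minus-younger gap. When the age mix is the same in every arm, the interaction noncentrality is

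λ = N · a(1−a) · Var_w(g) / SD²,

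with Var_w the arm-weighted variance of the gaps. Power comes from the noncentral F with 2 and N−6 df at α = 0.05.

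**Gaps from the plan's inputs (High-Touch, High-Tech, ODP).** PAM 8, 0, 1; SF-36 −8, −6, −1; readmission 0.04, 0.24, 0.14.

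**Step 1: reproduce the plan.** Six cells of 186 (1,120/6 = 186.7) give N = 1,116, a = 0.5, equal *w*, and N·a(1−a) = 279.
- PAM: Var = (25+9+4)/3 = 12.67; λ = 279 × 12.67/20.9² = 8.09; power 72.1% (72.3% at 186.7 per cell; stated 72.2%).
- SF-36: Var = (9+1+16)/3 = 8.67; λ = 279 × 8.67/100 = 24.18; power 99.5% (stated 99.5%).
- Readmission: Var = (0.01+0.01+0)/3 = 0.00667. The SD must be assumed. The six unweighted rates give 0.436 (averaging the variances) to 0.447 (from the mean rate). At 0.44, λ = 9.61 and power is 79.8% (stated 79.8%).

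**Step 2: the plan's own cells.** With a = 0.23 and *w* = 0.4, 0.4, 0.2, N·a(1−a) = 1,120 × 0.1771 = 198.35.
- PAM: weighted mean gap 3.4; Var = 0.4×4.6² + 0.4×3.4² + 0.2×2.4² = 14.24; λ = 6.47; power 61.7%.
- SF-36: weighted mean gap −5.8; Var = 0.4×2.2² + 0.4×0.2² + 0.2×4.8² = 6.56; λ = 13.01; power about 91%.
- Readmission: weighted mean gap 0.14; Var = 0.4×0.01 + 0.4×0.01 = 0.008. At SD 0.44, λ = 8.20 and power is 73% (71% to 74% for SD 0.447 to 0.436). With the SD pooled within the real cells (0.409), λ = 9.50 and power is 79%. A simulated logistic likelihood ratio test without covariates (20,000 runs) gives 69.2%, against 73.2% in equal cells of 187.

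Simulation of the ANOVA in the real cells agrees: PAM 61.8%, SF-36 90.9%.

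| Layout (N = 1,120) | PAM | SF-36 |
|---|---|---|
| Six equal cells | 72% | 99.5% |
| 2:2:1 only, ages 50/50 | 77.6% | 97.7% |
| 23/77 only, equal arms | 56.4% | 96.8% |
| 23/77 and 2:2:1 | 61.7% | 91% |

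For PAM the age split causes the loss; for SF-36 both departures contribute.

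**Step 3: do the two sets of inputs agree?** Overall value = a × older + (1−a) × younger, by arm (High-Touch/High-Tech/ODP):

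| | Main-effect input | At 50/50 | At 23/77 |
|---|---|---|---|
| Readmission | 20% / 28% / not stated | 20 / 28 / 35% | 18.9 / 21.5 / 31.2% |
| PAM | 4 / 8 / 0.5 | 4 / 8 / 0.5 | 1.84 / 8.00 / 0.23 |
| SF-36 | 11 / 5 / 0 | 11 / 5 / 0.5 | 13.16 / 6.62 / 0.77 |

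At 50/50 every stated main-effect value matches except SF-36 ODP (0.5 against 0). PAM High-Tech is 8 in both age groups, so it matches at any split. The other matches occur only at 50/50.

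**Step 4: consequence for the main comparisons.** Two-sample test of proportions, 448 per arm:
- 20% vs 28%: (0.08 − 1.96×0.02854)/0.02841 = 0.847; power 80%, as stated.
- 18.92% vs 21.52%: (0.026 − 1.96×0.02684)/0.02682 = −0.99; power about 16%.

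On the same subgroup inputs, High-Touch vs ODP readmission (448 vs 224) has about 94%, and the three-arm chi-squared test about 92% (stated 95%). The PAM High-Touch vs High-Tech difference becomes 8 − 1.84 = 6.16, with 99% power (stated 82%). SF-36 stays above 99%.

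**Step 5: the PAM wording.** With no High-Touch effect in younger participants and 8 in older ones, the overall mean is 0.23 × 8 = 1.84. An overall 4 would need 4/0.23 = 17.4 in older participants, which is not equal to High-Tech's 8.

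**The case against.** The strongest reply is that the averaging is disclosed. The figures are correct for the stated method, so this is an optimistic simplification rather than a slip. That is true of the arithmetic. It does not make the powers true of a design whose 23% and 2:2:1 are given in the same section.

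Four further points have weight:

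- **Readmission.** The SD of 0.44 is a value chosen because it returns 79.8%. With the SD pooled over the real cells, the ANOVA power is 79%, so no clear loss is shown by the plan's own method. This stands, and only a range can be given.
- **Covariate adjustment.** The planned models adjust for baseline covariates, and the calculations here, like the plan's, do not. If adjustment removed 5% to 20% of the residual variance (an assumption; the documents give no figure), PAM power would be 64% to 72%. The top of that range is needed just to regain the stated value.
- **Different scenarios.** Main-effect and interaction inputs cite different sources, and 80% for 20% vs 28% is correct. That statement is not wrong by itself. It cannot hold together with the subgroup rates and the 23%.
- **Limited consequence.** SF-36 stays above 90%, PAM was already shown below 80%, and some contrasts gain power. This bears on how serious the point is, not on whether it is right.

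**Conclusion.** The concern holds and should be fixed. At the plan's own cell sizes, PAM interaction power is about 62%, not 72.2%, and SF-36 about 91%, not 99.5%. Both use only the plan's means and SDs, in an unadjusted two-way ANOVA at N = 1,120 with the same age mix in each arm. Readmission is 69% to 79% against 79.8%, depending on the SD and on whether the ANOVA or the logistic test is used.

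The main-effect and age-specific scenarios cannot both be true at 23% older. If the age-specific one is true, the primary High-Touch vs High-Tech readmission comparison has about 16% power. The documents do not show which scenario is better supported, and this does not establish that the trial as a whole is underpowered.

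**What to change.** Choose one of two routes and revise the power paragraphs accordingly.

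**Option 1: keep the main-effect inputs.** Replace the age-specific inputs with one set whose 23/77 weighted averages equal the main-effect values for all three outcomes. Recompute with cells of 103/103/52 and 345/345/172, using the planned logistic test for readmission or stating the SD. If each arm's older-minus-younger gap is kept, λ for PAM and SF-36 does not change, so they remain at 62% and 91%.

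For readmission, keeping the gaps and assuming 35% overall in ODP gives 23.1/46.5/45.8% older and 19.1/22.5/31.8% younger. Power is then about 75% by ANOVA and 58% by the logistic test; an overall ODP rate of 33.2%, which reproduces the stated 95%, gives almost the same powers. This is an illustration, not a target: at 35% it puts High-Tech slightly above ODP in older participants, the reverse of the plan's 40% vs 42%. For PAM, either the verbal description or the High-Touch mean of 4 must change.

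**Option 2: keep the age-specific inputs.** Restate the interaction powers as about 62% (PAM), 91% (SF-36) and 69% to 79% (readmission, naming the SD and test). Add that under these inputs the primary High-Touch vs High-Tech readmission test has about 16% power, the three-arm readmission test about 92%, and the PAM contrast between the active arms about 99%.

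The cost is rewriting those paragraphs and showing some less favourable powers. Enrolment, estimands, tests and population are unchanged.

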We are only powering for the interactions with age, since we do not have any a-priori hypotheses about subgroup effects for the other variables. Those additional subgroups will clearly be labeled as exploratory and will only be examined further if the overall analysis is significant. We will conduct modeling as defined above to examine the HTE and will utilize contrasts from these regression models to make inferences about the heterogeneity. We will present both the treatment effect estimates, in terms of estimated odds or risk ratios for dichotomous or rate outcomes or the model coefficients for the continuous outcomes and measures of their variability in the form of confidence intervals. Two-sided tests of level 0.05 of the interactions between intervention and HTE subgroup will allow us to test the Aim 2 hypotheses.

For all the described models, we will focus on the 12-month outcome. Each of the above analyses will also be repeated using all follow-up outcomes collected as a secondary analysis using a mixed model with a random intercept to account for within-subject repeated measures and associated correlation. Significance tests from all regression models will all be assessed using likelihood ratio tests for logistic, Poisson, or, if applicable, negative binomial models or partial F-tests for linear regression.

Additionally, exploratory data analyses will include comparison of the following variables in the pre- versus post-COVID-19 time periods: a) demographics and primary outcomes at baseline, b) the primary outcomes over time, and c) patterns in missing data. If significant differences result, we will repeat the primary analysis by: a) adjusting for the demographic variables that can describe pre- and post-COVID-19 participants, b) include indicator variables for post-COVID-19 enrollment with and without interactions with time variables, and c) statistically account for missing patterns.

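### The 79.8% power for the age-by-treatment interaction on readmission belongs to an ANOVA on risks with equal cells; the planned logistic likelihood ratio test has about 69-70% at the planned cells, unadjusted

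*Combined protocol and SAP*

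**What the plan says.** The power side is in the combined protocol and SAP, *Sample Size and Power Calculations*. Interaction power is computed for a two-way factorial layout using the average group size. For readmission the SD comes from a normal approximation, and the authors "applied a 2-way ANOVA as similar procedures are not available for dichotomous outcomes without approximating as normal". The result is: "we have 79.8% power to detect a significant interaction with readmission rates of 22%, 40%, and 42% in the older group" (High-Touch, High-Tech and ODP in that order), with "rates of 18%, 16% and 28% in the younger group". The section assumes "a total of 1,120 participants at 12-month postenrollment data collection time point", allocated 2:2:1, with 23% aged 60 or above. Age is the only interaction that is powered; the others are labelled exploratory.

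The analysis side is in *Quantitative Analysis*. Dichotomous outcomes go to logistic regression with covariates, and Aim 2 adds a treatment-by-subgroup interaction. The plan specifies "Two-sided tests of level 0.05 of the interactions between intervention and HTE subgroup", and significance is "assessed using likelihood ratio tests for logistic, Poisson, or, if applicable, negative binomial models".

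**The concern.** A two-way ANOVA on 0/1 outcomes asks whether risk differences vary by age. The interaction term in a logistic model asks whether odds ratios vary by age. These are different null hypotheses, and at a given set of six rates the two tests have different power. The plan discloses a normal approximation, but it does not mention the change of scale and gives no power for the logistic test.

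The powered layout also has six equal cells. The trial will have a small older stratum and a half-sized ODP arm.

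At stake is how the Aim 2 age result for the plan's main outcome is read. A reader of a non-significant interaction would assume about a one in five chance of missing the hypothesised pattern (100 − 79.8 = 20.2%). For the planned test at the planned cells it is nearer three in ten (100 − 69.4 = 30.6%).

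**Working it through.** **Inputs from the documents.** Older rates 0.22, 0.40, 0.42; younger rates 0.18, 0.16, 0.28; analysed N 1,120 (already net of 20% attrition); arms of 448, 448 and 224; 23% aged 60 or above; two-sided 0.05. A treatment-by-age interaction with three arms and two age groups has 2 df. The SD used is not stated, so it is an assumption below.

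**1. Reproduce the stated figure.** The average cell is 1,120/6 = 186.7. Arm means over the two age groups are 0.20, 0.28 and 0.35, and the age effect is ±0.07. The interaction residuals in the older row are −0.05, +0.05 and 0, with opposite signs in the younger row, so their sum of squares is 4 × 0.0025 = 0.01. The noncentrality is λ = n × 0.01/SD². With n = 186 and SD 0.44, λ = 1.86/0.1936 = 9.61, and the 2-df noncentral F gives 79.8%.

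Sensitivity to the SD: binomial choices of 0.436 to 0.447 give 78.4% to 80.8%. The wider range of 0.417 to 0.449 gives about 84% down to 78%.

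The same method with n = 186 gives 72.1% for PAM (λ = 186 × 19/20.9² = 8.09; stated 72.2%) and 99.5% for SF-36 (λ = 186 × 13/10² = 24.18; stated 99.5%). This confirms that the plan used a 2-df test and equal average cells.

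**2. Planned test, equal cells.** Fit the logistic model without interaction to the expected counts, giving fitted risks m. Then λ = 2 Σ n [p ln(p/m) + (1−p) ln((1−p)/(1−m))], and power is the chance that a noncentral chi-square on 2 df exceeds 5.99.
- Fitted risks: older 0.257, 0.352, 0.431; younger 0.143, 0.208, 0.269.
- At 186.7 per cell, λ = 8.16 and power is 72.7%. Simulation with 20,000 trials gives 73.2% to 73.4%.
- On the same simulated data the linear ANOVA rejects in 82.2% to 82.6%. At equal cells the loss therefore comes from the scale, not from treating 0/1 data as normal.

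**3. Planned test, planned cells.** Older: 0.23 × 448 = 103.0 twice, and 0.23 × 224 = 51.5. Younger: 345.0 twice, and 172.5. This assumes the same age mix in each arm, as randomisation gives on average.
- Fitted risks: older 0.287, 0.322, 0.443; younger 0.160, 0.183, 0.273.
- λ = 7.61 and power is 69.4% (simulation 70.0%).

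**4. Risk-difference test at the planned cells.** The older-minus-younger differences are 0.04, 0.24 and 0.14. Their variances, each the sum of p(1−p)/n over the two ages, are 0.00209, 0.00272 and 0.00590. Inverse-variance weights are 477.7, 367.8 and 169.6, with weighted mean 0.129. Then λ = 477.7 × 0.0892² + 367.8 × 0.1108² + 169.6 × 0.0108² = 8.34, and power is 73.6%.

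**5. Split of the shortfall.** The total is 79.8 − 69.4 = 10.4 points. At the planned cells, scale accounts for 73.6 − 69.4 = 4.2 points. The other 79.8 − 73.6 = 6.2 points come mainly from averaging the cells.

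The split depends on order and comparator. Changing scale first, at equal cells, gives 79.8 − 72.7 = 7.1 points for scale and 72.7 − 69.4 = 3.3 for cell sizes. A pooled-variance ANOVA at the planned cells still rejects in 79.2% of simulated trials. However, its pooled variance there is about 0.409² = 0.167, below the 0.172, 0.240 and 0.244 of the small older cells, so it is not used as the benchmark. The 69-70% does not depend on the split.

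**The case against.** **The figure is right for its stated method.** True. The method, the normal approximation and the averaged cells are all disclosed. A reader might infer that the plan made an arithmetic error; it did not. The disclosure does not, however, tell anyone that the analysis is on another scale.

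**The sentence on availability may describe the software.** The plan says all power estimates came from PASS version 13, and the remark can be read as a limit of that tool. That is a fair reading, so the wording needs tightening and is not evidence of a deeper fault.

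**The planned analysis should move to risk differences.** A reader might infer this, because the hypothesis is stated in rates and Aim 2 is meant to inform targeting of resources. The documents do not support treating the odds-ratio test as a mistake. It is prespecified, the plan reports odds or risk ratios with confidence intervals, and a change of scale would change the estimand. The plan's rates also show interaction on both scales. High-Touch against High-Tech goes from +2 points in younger members to −18 in older members, with a ratio of odds ratios of 0.37. Risk differences are not uniformly more sensitive either: for High-Tech against ODP by age at the planned cells, Wald power is about 33% on log-odds and 19% on risk differences.

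**Single contrasts may do better.** The plan mentions contrasts. By a Wald approximation, High-Touch against High-Tech by age on log-odds has about 77% at the planned cells and 79% at equal cells. But the stated 79.8% describes the overall 2-df interaction.

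**The consequence is modest.** This stands. The plan openly accepts 72.2% for the PAM age interaction, and the trial's primary power rests on another comparison.

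**Conclusion.** The mismatch is real and of moderate size. The planned test has about 73% power at equal cells and about 69-70% at the planned cells, against a stated 79.8%. Even a risk-difference test at the planned cells would have only about 74%, so a change of scale alone would not recover the stated figure.

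These results rest on the plan's six rates, the 1,120 analysed, the same 23% older share in every arm, and the overall 2-df test. Reproducing 79.8% also assumes an SD near 0.44, but the logistic figures do not use that SD. They are unadjusted, whereas the planned model includes age, race, gender, insurance type, illness complexity and socio-economic status. Adjusted power cannot be computed from the documents and could differ.

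A reader might infer that the trial as a whole is underpowered. Nothing here bears on the main High-Touch against High-Tech readmission comparison, which has its own calculation: 448 per arm with 20% against 28% gives 80.2%, in line with the stated 80%.

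**What to change.** In *Sample Size and Power Calculations*:

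- Restate the readmission interaction power as about 69-70% for the 2-df logistic likelihood ratio test at 2:2:1 allocation with 23% aged 60 or above. Give about 73% as the equal-cell value, and mark both as unadjusted for covariates.
- Reword the remark on availability. A noncentral chi-square on the model deviance, or simulation, gives the power for the binary outcome directly. If the remark meant the named software, say so.

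In *Quantitative Analysis*, keep the odds-ratio interaction as the Aim 2 test. As an optional addition, report age-specific risk differences with confidence intervals from the same model, to serve readers interested in absolute benefit.

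The cost is a few sentences of SAP text and a short calculation, with no change to design, data or the planned test. The downside is that the stated power becomes less favourable.

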#### Aims

This study aims to compare the effectiveness of the approaches on patient-centered outcomes and determine which care strategy works best for whom and under what circumstances. By observing comparisons on key outcomes with ODP, our findings will enable patients and health care systems to understand the relative effectiveness of the care strategies vis-à-vis current practice and provide much-needed information for patients with MCC as well as health systems striving to support them more effectively and efficiently.

**Primary Aim 1**: Compare the effectiveness of High-Touch, High-Tech, and ODP on primary outcomes including hospital readmission, health status, and patient activation, and on several

secondary outcomes including functional status, quality of life, care satisfaction, emergent care use, engagement in primary, specialty, and mental health care, and gaps in care.

*Hypothesis 1a:* High-Touch will result in lower readmission rates at 12 months compared to High-Tech & ODP.

*Hypothesis 1b:* High-Touch will result in higher health status at 12 months compared to High-Tech & ODP.

*Hypothesis 1c:* High-Tech will result in higher patient activation at 12 months compared to High-Touch & ODP.

**Primary Aim 2**: Examine the differential effects of the interventions for patient subgroups, based on age, race, illness complexity, and comorbid behavioral health conditions to evaluate heterogeneity of treatment effects (HTE) and determine for whom and under what circumstances the interventions are most effective.

Hypothesis 2a: For all primary outcomes, High-Touch will have greater positive impact than High-Tech & ODP for older participants (60 years or more) and for participants with comorbid behavioral health conditions.

**Primary Aim 3**: Examine perceived barriers and facilitators to efficient and effective implementation of High-Touch and High-Tech interventions for delivering evidence-based integrated care.

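### For patient activation (PAM), the planning values contradict Hypothesis 2a in participants aged 60 or more, and the interaction test named for Aim 2, with its stated power, does not address that hypothesis

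*Combined protocol and SAP*

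**What the plan says.** **Hypothesis.** Under Aims, Hypothesis 2a covers all primary outcomes (readmission, SF-36, PAM) and says that "High-Touch will have greater positive impact than High-Tech & ODP for older participants (60 years or more"), and likewise for participants with comorbid behavioral health conditions. Only the age part is at issue here.

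**Planning values.** Sample Size and Power Calculations gives the expected age-by-treatment pattern, in the order High-Touch, High-Tech, ODP:
- PAM: the text says that "in the older group, the interventions will work equally well and much more effectively than ODP". The values are "mean increases in PAM of 8, 8, and 1 in the older group for High-Touch, High-Tech, and ODP", and "mean increases of 0, 8 and 0 in the younger group". For these, "we have 72.2% power to detect a significant interaction".
- SF-36: "mean increases in SF-36 of 7, 2, and 0 in the older group", and "mean increases of 15, 8, and 1 in the younger group", with a stated power of 99.5%.
- Readmission: 22%, 40% and 42% in the older group and 18%, 16% and 28% in the younger group, with a stated power of 79.8%.

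**Test.** Quantitative Analysis says: "Two-sided tests of level 0.05 of the interactions between intervention and HTE subgroup will allow us to test the Aim 2 hypotheses". The same section says that contrasts from the regression models will be used for inference about heterogeneity, and that effect estimates will be shown with confidence intervals. It lists no contrast and links none to Hypothesis 2a.

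**The concern.** Aim 2 is a primary aim, and age is the only subgroup factor for which the plan gives power. Two things do not fit together.

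First, Hypothesis 2a needs High-Touch to be superior to High-Tech in older participants on PAM, while the power section expects no difference there. Both cannot be the plan's expectation.

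Second, the test assigned to the Aim 2 hypotheses asks only whether the pattern across three arms differs between age groups. It can be significant when High-Touch has no advantage in older people, or when its advantage is larger in younger people. Without named, signed contrasts, a significant interaction could be reported as confirming Hypothesis 2a when the data do not show it. A reader could also take 72.2% and 99.5% as the chance of confirming the hypothesis, which they are not.

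**Working it through.** **Inputs.** Evaluable sample sizes of 448/448/224 (1,120 in total), 23% aged 60 or more, SD 20.9 for PAM and 10 for SF-36, two-sided alpha 0.05, and interaction power based on a two-way factorial with average cell size. All come from Sample Size and Power Calculations, except alpha, which is in Quantitative Analysis.

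**1. The plan's own figures.** The average cell is 1,120/6 = 186.7. For the 2-df interaction F test, λ = n × Σ(interaction effects²)/SD², where an interaction effect is the cell mean minus row mean minus column mean plus grand mean.
- PAM: the older-group effects are 2.5, −1.5, −1.0 and the younger-group effects are their negatives, so the sum of squares is 2 × (6.25 + 2.25 + 1) = 19. With n = 186, λ = 186 × 19/20.9² = 8.09 and power is 72.1%. With n = 186.7 it is 72.3%. Stated: 72.2%.
- SF-36: the effects are −1.5, −0.5, 2.0 and their negatives, so the sum is 2 × (2.25 + 0.25 + 4) = 13. λ = 186 × 13/10² = 24.18 and power is 99.5%. Stated: 99.5%.

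Both figures are correct as power for the global interaction test with equal cells.

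**2. What the planning values imply for High-Touch.** Positive means that High-Touch is better. Readmission is in percentage points.

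| Outcome | Comparator | Age 60+ | Under 60 | Older minus younger |
|---|---|---|---|---|
| Readmission | High-Tech | +18 | −2 | +20 |
| Readmission | ODP | +20 | +10 | +10 |
| PAM | High-Tech | 0 | −8 | +8 |
| PAM | ODP | +7 | 0 | +7 |
| SF-36 | High-Tech | +5 | +7 | −2 |
| SF-36 | ODP | +7 | +14 | −7 |

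The PAM interaction arises because High-Touch is expected to do nothing in younger people and to draw level with High-Tech in older people. It never moves ahead.

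**3. Power for the comparisons at age 60 or more.** Assuming that 23% applies in each arm, the cells are 0.23 × 448 = 103 and 0.23 × 224 = 52 (rounded).
- PAM against High-Tech: the difference is 0, so the rejection probability is alpha, 5%.
- PAM against ODP: SE = 20.9 × √(1/103 + 1/52) = 3.56; 7/3.56 = 1.97; power about 50%.
- SF-36 against High-Tech: SE = 10 × √(2/103) = 1.39; 5/1.39 = 3.59; power about 95%.
- SF-36 against ODP: SE = 10 × √(1/103 + 1/52) = 1.70; 7/1.70 = 4.11; power about 98%.
- Readmission against High-Tech: pooled rate 31%, null SE 0.0644, alternative SE 0.0632; (0.18 − 1.96 × 0.0644)/0.0632 = 0.85; power about 80%.
- Readmission against ODP: pooled rate 28.7%, null SE 0.0770, alternative SE 0.0797; (0.20 − 1.96 × 0.0770)/0.0797 = 0.62; power about 73%.

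**4. The age difference in the High-Touch minus High-Tech contrast**, with 345 per active arm under 60:
- PAM: +8, SE = 20.9 × √(2/103 + 2/345) = 3.32; power about 67%, in the hypothesised direction.
- SF-36: −2, SE = 10 × √(2/103 + 2/345) = 1.59; two-sided rejection probability about 24%. Nearly all of that lies in the direction opposite to a larger older-age advantage; only about 0.06% lies in the direction of one.

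**The case against.** The best defence has three parts.

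**Wording of the powers.** The plan describes 72.2% and 99.5% only as power to detect an interaction, and both are right as such. It states the PAM equality and the larger SF-36 effect in younger people openly. This stands: there is no miscalculation. The link to Hypothesis 2a comes from the sentence in Quantitative Analysis that assigns the Aim 2 hypotheses to the interaction tests.

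**Contrasts are already mentioned.** Quantitative Analysis commits to model contrasts and confidence intervals, so inference need not rest on a global p-value alone. This stands in part and lowers the risk. But the contrasts, their direction and their tie to Hypothesis 2a are not given, and no power is stated for them.

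**SF-36 may be consistent.** A reader might infer that the SF-36 values contradict Hypothesis 2a as well. The documents do not support that. Read as a ranking within older people, which is closest to the wording under Aims, 7 > 2 > 0 agrees with the hypothesis. The SF-36 values run the other way only if the hypothesis means a larger advantage in older than in younger people (5 against 7 versus High-Tech, 7 against 14 versus ODP). On that second reading the PAM values have the hypothesised sign (+8 and +7). No single reading makes both outcomes fail.

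**Conclusion.** The point holds in a limited form. On PAM, Aims and the power section contradict each other about High-Touch against High-Tech at age 60 or more if Hypothesis 2a is a ranking within older people, as its wording suggests. On either reading, the test named for Aim 2 does not by itself test Hypothesis 2a, because a significant 2-df interaction carries no direction.

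The stated 72.2% and 99.5% are therefore not power for that hypothesis. At the plan's values the older-group comparisons have about 80%, 5% and 95% power against High-Tech, and 73%, 50% and 98% against ODP (readmission, PAM, SF-36). These figures assume that the 23% share applies equally in each arm, that the planned SDs hold within age groups, and that there is no covariate adjustment or multiplicity correction.

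It would go too far to say that the power figures are wrong, or that the SF-36 values contradict the hypothesis outright. The documents support neither.

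**What to change.** In the SAP:
- State that Hypothesis 2a is tested, for each primary outcome, by the contrasts High-Touch against High-Tech and High-Touch against ODP among participants aged 60 or more, both taken from the interaction model.
- Report the older-minus-younger difference of each contrast, with its sign and confidence interval.
- Keep the 2-df interaction test as a global test of heterogeneity only.
- Restate power for the named contrasts.
- Reconcile Aims with the power section on PAM by limiting Hypothesis 2a for PAM to what the plan expects, for example High-Touch over ODP. The planning values should not be altered to fit the hypothesis.

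The cost is SAP wording and recalculated power, with no change to design or data collection. The price is a less favourable PAM figure: about 50% for High-Touch against ODP at age 60 or more, in place of 72.2%.
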